### **c. Secondary Objectives/Aims**

#### **AIM 2: Compare MBC fidelity post IMPACT Center methods deployment versus historical controls.**

We will evaluate at the clinic level whether IMPACT methods were effective in optimizing MBC fidelity. To do this, we will employ two methods: 1) an **anonymous self-report survey** pre-implementation, 3 months and again 6 months post implementation strategies, and 2) a historical control design comparing MBC fidelity pre- and post- IMPACT methods (e.g., design kits). **Pre-IMPACT method** data will be captured from a pre-existing, routinely gathered, de-identified database from the Washington State CBT+ initiative (**further described in Section 6 – Setting**). The database will represent MBC fidelity 2 years prior to IMPACT center methods. For **post-IMPACT method** data, at least 5 therapists at each clinic will be asked to report MBC fidelity data to the Washington State CBT+ Initiative Dashboard for up to 5 cases. Therapists at each clinic are familiar with the Dashboard, as its use is part of their routine training. Data recorded related to MBC fidelity consists of therapist's use of the three main components of MBC – (1) Collect, (2) Share, and (3) Act (described further in **Scientific Background** and **Study Procedure** sections).

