**Aim 2 (A2): Compare MBC fidelity post IMPACT Center methods deployment versus historical controls (no site visit)**

The purpose of IMPACT methods is to improve clinician's fidelity using MBC. Fidelity will be conceptualized as therapist's use of the three main components of MBC – (1) Collect, (2) Share, and (3) Act. We will assess fidelity in two ways. First, we will use a brief anonymous self-report survey before implementing strategies and 6 months after. Previously, we had planned to use data from the Washington State CBT+ Initiative Dashboard, but we have had difficulty recruiting clinicians to engage in this task. For our second method of fidelity measurement we will ask clinics to send a dataset from their electronic health record for at least 6 months before IMPACT methods were deployed, and to 6-months after the active implementation period. The dataset will not contain any PHI. We will compare historical data at 6- and -18 months post site visits. .

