### AIM 2: Compare MBC fidelity post IMPACT Center methods deployment versus historical controls (not associated with a site visit)

NIMBLE will compare data at a clinic level prior to MBC training and at 6- and 18-months post site visit 1.

Our approach is to evaluate, at a clinic level, use of MBC before and after IMPACT method deployment. Specifically, we focus on whether therapists engaged in the main components of MBC: (1) Collect, or how often measures were provided to patients (frequency of administration), (2) Share, or how often therapists discuss outcome measures with their patients, and (3) Act, or whether therapists and patients used outcome measure data to change their direction in therapy (reevaluation using data).

We will use two different methods to assess use of MBC. The first is a short anonymous self-report survey filled out before implementing new strategies to address barriers to MBC use, and a second time 6 months after implementation. The second method is to ask for 5 therapists to enter data from 5 cases related to MBC use into the Washington State CBT+ Dashboard. Data will be aggregated at the clinic level, as we are investigating whether IMPACT methods impact clinic-wide changes. We are not studying whether any individual person's behavior changes as a result of IMPACT methods.

Clinic staff/Therapists (N=30) across 4 CMHCs in Washington state.

Inclusion: Must be aged 21+ and be working at a CMHC that is participating in the WA State CBT (Cognitive Behavioral Therapy) + Initiative.

Exclusion: Must be willing to participate in study activities

Youth participants: NA, there are no Youth Participants in this aim

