**Clinic Staff and Therapist Consent Process**

The NIMBLE team at KPWHRI and Brown University will begin the consent process on the initial visit to each CMHC. The first activity in the visit is a training workshop which focuses on the importance of MBC. This workshop is desired by each of the CHMC and leadership at each CHMC have deemed this a required workshop for all staff providing clinical services to youth. Of note, even though the MBC workshop is mandatory for therapists, the rest of the study activities are not. The study team will elicit questions and ensure that all staff and therapists understand what participation entails. To minimize the possibility of coercion or undue influence, the study team will ask those interested in learning more to remain in the room, while those not interested will be asked to leave, at which point the study team will complete the oral consenting process there. Over the course of the study, the team will revisit the activities with participants and make sure they still are comfortable participating. For in-person site visits to ensure that staff and therapists are comfortable with our team's presence in the clinic during clinic observation activities we will implement the following procedures:

1. Announce that the meeting/huddle is being observed at the start of the meeting. Explain what type of information will be noted as part of the observation (i.e., workflows, relationships, direct anonymized quotes, etc.). Give people the opportunity to “opt-out” at the earliest possible time in the meeting/huddle.
2. Putting a sign on the door or in the room, or both, explaining that this meeting is being observed as part of an ethnographic study. Notes are being taken about MBC topics. If you would prefer to not be included in the notes, please contact study team member ([name] or [name]) (will provide photos of team members). This ensures people that came in late are aware they are part of a study and know how to opt out.
3. Remind folks at the end of the meeting that this session was observed, and notes made about MBC specific topics, and how to opt out.

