UPDATES: We deviated from the original analytic plan because we were unable to recruit clinicians to track outcome data using the CBT+ toolkit. Instead, and as documented in the protocol, we sent providers a Qualtrics form asking them to self-report their caseload as well as the number of clients they reported using measurement-based care with. The updated analytic plan based upon this change is as follows: Descriptive statistics will be used to summarize fidelity to measurement-based care (MBC) at each of the three assessment time points. A repeated-measures analysis of variance (ANOVA) will be conducted to evaluate whether fidelity to key components of MBC changes over time—from baseline (defined as 6 months post-enrollment) to 3 months after the conclusion of active implementation, and again at 6 months post-implementation. No statistical corrections for multiple comparisons will be applied given the single statistical test being carried out. Statistical significance will be evaluated at the 0.05 level (two-tailed). To address missing data, a conservative **Last Observation Carried Forward (LOCF)** approach will be used, allowing participants with partial data to be retained in the analytic sample. Assumptions of normality and sphericity will be assessed. If the assumption of sphericity is violated, Greenhouse-Geisser corrections will be applied. Effect sizes (e.g., partial eta squared) will be reported to estimate the magnitude of observed effects. All analyses will be conducted using R v4.3.3 and Rstudio 2023.12.1].

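### The SAP dates its baseline six months from an undefined enrollment, so its only test has no consistent pre-IMPACT reference and cannot deliver Aim 2's before/after comparison

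*SAP*

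**What the plan says.** The updated plan in the SAP (paragraph headed UPDATES) replaces the mixed model with one repeated-measures ANOVA on a provider self-report form. The three waves run from "baseline (defined as 6 months post-enrollment) to 3 months after the conclusion of active implementation, and again at 6 months post-implementation". Multiplicity is set aside "given the single statistical test being carried out". No other data source is analysed.

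The protocol gives Aim 2 two fidelity methods, with different reference points:

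- **Survey.** Section 2c schedules it "pre-implementation, 3 months and again 6 months post implementation strategies". Section 4 (Aim 2) says "we will use a brief anonymous self-report survey before implementing strategies and 6 months after". Sections 5a and 8a also place the first wave ahead of the strategies or the active implementation period.
- **Pre-IMPACT data.** Section 2c describes "a historical control design comparing MBC fidelity pre- and post- IMPACT methods (e.g., design kits"). Section 4 (Aim 2) says dashboard entry proved hard to recruit for, and substitutes a clinic health-record extract reaching back at least 6 months before IMPACT methods. Section 5a (Aim 2) states: "NIMBLE will compare data at a clinic level prior to MBC training and at 6- and 18-months post site visit 1". Section 8b applies the same analysis to each fidelity tool.

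On the order of events, section 7b says of the initial visit: "The first activity in the visit is a training workshop which focuses on the importance of MBC". Clinic leadership requires that workshop for staff who treat youth, and oral consent follows it. Section 7a adds that willingness to join Aim 2 is asked at the end of each Aim 1 interview.

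**The concern.** Aim 2 is titled as a comparison of fidelity after IMPACT methods with historical controls. A comparison of that kind needs an observation from before those methods. The SAP counts its first wave from enrollment, without saying whose enrollment and without tying the date to the training, the site visits or the start of strategies.

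Any fidelity change between the pre-IMPACT period and that wave is then left out of the estimate. A flat result could be reported as IMPACT methods having no effect, or a rise as improvement from before to after IMPACT. The planned test supports neither statement. Because the interval from enrollment is fixed, the wave could also fall after strategies have begun in a fast clinic. In that case even the change over strategy deployment would be measured from a contaminated starting point.

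**Working it through.** The point rests on timing, so the main check is arithmetic on protocol Table 2.

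**Inputs.** Clinic enrollment occupies months 0-6. Participant enrollment and site visits 1-3 share one 6-month block per cohort: months 6-12, 12-18 and 18-24 for cohorts 1, 2 and 3. (Section 4 speaks of two cohorts and Table 2 of three; the reasoning for each cohort is the same.) SAP baseline = enrollment + 6 months.

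| Cohort | Visits 1-3 | Baseline if participant enrollment | Baseline if clinic enrollment |
|---|---|---|---|
| 1 | 6-12 | 6+6 to 12+6 = 12-18 | 0+6 to 6+6 = 6-12 |
| 2 | 12-18 | 12+6 to 18+6 = 18-24 | 6-12 |
| 3 | 18-24 | 18+6 to 24+6 = 24-30 | 6-12 |

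**Participant enrollment.** The earliest possible baseline equals the end of the visit window in every cohort (12, 18 and 24). If visits keep to Table 2, the wave comes after the training, ethnography, barrier prioritization and causal pathway diagramming. The training already precedes consent (section 7b).

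**Clinic enrollment.** The wave coincides with cohort 1's visit window. It falls 12-12 = 0 to 12-6 = 6 months before cohort 2's window opens, and 18-12 = 6 to 18-6 = 12 months before cohort 3's. The same label would then pool different phases of the study.

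**Strategy start.** The documents give no date for site visit 3 within its block and no date for the first strategy launch. A fixed interval from enrollment therefore cannot be shown to precede the strategies in each clinic. Nor do the documents show that it followed them.

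**What the ANOVA can see.** Write the total change as

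(last wave - pre-IMPACT) = (baseline - pre-IMPACT) + (last wave - baseline).

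Under the participant-enrollment reading the SAP estimates only the second bracket. If a share f of the total change D occurs before baseline, the test sees D(1 - f).

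The documents give no f. The only effect sizes they state are the detectable range d = .36-.48, which belongs to the original mixed model; none is given for the ANOVA. A rough check with 30 therapists, 5 cases each per period, and (1.960 + 0.842) x sqrt(2 x DEFF x (1 - .15^2)/150), where DEFF = 1 + 4 x ICC, gives:

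- ICC .01: DEFF = 1.04, d = .326
- ICC .30: DEFF = 2.20, d = .474

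The upper end is close to the stated .48 and the lower end is not close to .36. The plan does not list all its inputs, so its range can be neither confirmed nor called wrong. Taking .48 purely as a scale, with f assumed:

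| f | 0 | .25 | .50 | .75 | 1 |
|---|---|---|---|---|---|
| d visible to the ANOVA | .48 | .36 | .24 | .12 | 0 |

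**Other analyses.** The SAP says clinicians could not be recruited to track cases in the CBT+ toolkit, so the follow-up half of the dashboard comparison is gone. The health-record extract is the remaining pre-IMPACT source with planned follow-up, and the updated SAP does not mention it.

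**The case against.** The strongest reply is that the survey is being held to the other method's reference point. Throughout the protocol its first wave is meant to precede strategies, not training. On the participant-enrollment reading, month 6 is roughly the end of planning, which broadly fits. Training is also not among the IMPACT methods listed for Aim 1, and a post-training first wave keeps an immediate training gain out of the strategy effect. All of this stands. A reader might infer that the ANOVA cannot address Aim 2 at all, but the documents do not support that: it can speak to the survey part of Aim 2.

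Three other strong readings also fail:

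- **That no pre-IMPACT observation can exist.** Under clinic enrollment, the wave would precede the visits of cohorts 2 and 3.
- **That section 5a's 6-month follow-up contradicts the SAP's 6-month baseline.** Section 4 attaches the 6- and 18-month points to the historical data, and section 5a describes the survey separately. The passages need clarifying, but a contradiction is not shown.
- **That the under-15% figure in section 2a gives a starting level from which to compute the loss.** It is a general share of therapists using MBC as recommended. The SAP outcome concerns clients within a provider's caseload.

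The reply does not supply a dated pre-strategy wave, and it does not supply an SAP analysis of the pre-IMPACT data.

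**Conclusion.** The concern holds in a limited form. As written, the SAP's single test has no consistent pre-IMPACT reference and no guaranteed pre-strategy reference. It can at most describe change over strategy deployment. It cannot deliver Aim 2's comparison of fidelity before and after IMPACT methods, and nothing else in the updated SAP does.

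The finding that baseline follows the training and visits 1-3 assumes that enrollment means participant enrollment and that visits ran to Table 2. The finding of different phases by cohort assumes clinic enrollment. The lack of a consistent reference holds on both. The size, and even the direction, of any change absorbed before baseline is unknown from the documents. A reader might infer that the result will be biased toward no effect by some stated amount; nothing in the plan supports a figure.

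**What to change.** 1. In the SAP, define the first wave as post-training and pre-strategy. Anchor it to each clinic's first strategy launch, and flag clinics or responses where it fell later.
2. State that the survey ANOVA estimates change over strategy deployment only and does not test IMPACT methods against a pre-IMPACT level.
3. Add an analysis of the health-record data described in section 4 (Aim 2), with the pre-training period as reference, for whichever of Collect, Share and Act those data capture. The documents do not show that all three are covered. Otherwise, state that the comparison before and after IMPACT is dropped.
4. In sections 4 and 5a, say which data source the 6- and 18-month points concern, so that they are not confused with the survey waves.

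Items 1, 2 and 4 are wording plus a check of dates. Item 3 needs an analysis of data the protocol already plans to request. The downside is a narrower claim from the survey. A pre-training survey wave would be better still, but it is possible only in a clinic that has not yet started, and the SAP says forms have already been sent.

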### 2. Objectives

#### a. Purpose

Measurement Based Care (MBC) is the systematic, routine evaluation of symptoms to inform care decisions. Especially in youth, MBC increases the rate of symptom improvement, detects clients who would otherwise deteriorate, and alerts therapists to non-responders. Despite its demonstrated utility, MBC is rarely implemented with fidelity; fewer than 15% of therapists report using MBC per recommendations. Previous efforts to support MBC implementation have yielded suboptimal outcomes because Community Mental Health Clinic (CMHC) leaders are challenged to identify and prioritize barriers and select strategies to overcome them. New methods are needed to optimize MBC implementation and treatment quality to improve youth mental health outcomes in community settings. The purpose of this project (referred to as NIMBLE) is to pilot test and refine IMPACT Center methods in six diverse CMHC clinics across Washington state (three of six serve primarily Latinx populations) to optimize MBC implementation.

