**A1f. Focus Groups to Improve IMPACT methods.** We will engage our partners in a semi-structured focus group to capture their experience engaging in all IMPACT Center methods in the 3 site visits to inform further toolkit refinement. A facilitator not previously engaged in any of the activities will conduct a 90-minute focus group to solicit reactions to all aspects of IMPACT's methods, including the steps and personnel requirements of each method, and their output (e.g., prioritized barriers; utility of the information captured in the CPDs). We will also be collecting implementation outcome measures, Acceptability, appropriateness, feasibility using established measures. The focus group data will supplement observer notes taken throughout the site visits.

To gather quantitative data related to IMPACT methods, up to N = 30 workshop participants will also be asked to complete Weiner et al.'s (2017) acceptability of intervention measure (AIM), feasibility of intervention measure; (FIM), and intervention appropriateness measure (IAM). The focus of these measures will be on assessing the acceptability, feasibility, and appropriateness of IMPACT center methods (e.g., design kits). These measures are uploaded in the IRBNet submission.

**AIM 2 (A2): Compare MBC fidelity post IMPACT Center methods deployment versus historical controls.** To examine MBC fidelity in Aim 2, we use routine session process data entered by therapists as part of their participation in the Washington CBT+ Initiative. In addition, we will request that therapists fill out a short anonymous self-reported survey on outcome use before the active implementation period, at 3 months and again at 6 months (REDCap survey: MBC Outcome Questionnaire).

[name] is a co-director of the Washington State CBT+ Initiative and the MPI of the IMPACT center. The dashboard with de-identified cases from which we are collecting data from is maintained as part of the CBT+ Initiative, and the CBT+ Initiative is the primary "laboratory" for IMPACT center methods. When data from CBT+ aligns with IMPACT aims, data can be curated by their team and sent to IMPACT NIMBLE co-investigator [name], via secure file transfer per CBT+ operational guidelines and procedures. Data will be shared back with clinics and the CBT+ initiative only in aggregate form for the purposes of quality/continuous improvement. CBT+ has routinely used data from the dashboard for quality improvement over the past 10 years.

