#### **b. Storage of data and/or specimens.**

All data will be stored on password-protected computers on the study G-drive accessible only to IMPACT Center Study Staff or on the KPWA REDCap platform. Physical documents will be stored at MPE in locked filing cabinets only accessible to study staff. All materials will be de-identified, using a unique study ID that does not require a crosswalk because we only need to know which

documents correspond with each other. Because this is de-identified data, it will be kept indefinitely. Postage paid self-addressed sealed envelopes will be sent back by USPS. All audio and digital recordings of rapid ethnography interviews will be kept on the G-drive or Sharepoint site with access only granted to research staff on the IRB.

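### The SAP calls LOCF conservative without support: in this single-group comparison its bias can run in either direction

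*SAP*

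**What the plan says.** The analysis now in force is under UPDATES in the SAP dated 5/5/2025. Therapists report by survey ("we sent providers a Qualtrics form asking them to self-report their caseload", together with the number of clients with whom they used MBC). Fidelity is then compared across three time points with one repeated-measures ANOVA, two-tailed at 0.05, with Greenhouse-Geisser correction if sphericity fails.

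On missing data the SAP says "To address missing data, a conservative Last Observation Carried Forward (LOCF) approach will be used", and the reason given is "allowing participants with partial data to be retained in the analytic sample". Fidelity is to be summarised at each time point, and "Effect sizes (e.g., partial eta squared) will be reported to estimate the magnitude of observed effects".

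For Aim 2, Protocol section 5a gives "Clinic staff/Therapists (N=30) across 4 CMHCs in Washington state", while section 2a sets out to "pilot test and refine IMPACT Center methods in six diverse CMHC clinics across Washington state". Neither document gives an expected non-response rate, a reason why forms would be missing, an expected course of fidelity, a meaning for conservative, or a sensitivity analysis.

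**The concern.** The label tells a reader that any error from LOCF is on the safe side, so that a reported gain can be read as a lower bound. That would need fidelity to stay level or rise after the last form received, or non-response to follow a particular pattern. The documents give grounds for doubt on both:

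- **Course.** The SAP places both follow-up forms after active implementation ends, so fading is possible. Protocol section 2b lets clinics switch strategies at 3 months if MBC has not improved, so the course may also change for that reason.
- **Response.** The SAP reports that clinicians could not be recruited for the earlier fidelity task. That low users of MBC would be less likely to return a form about MBC is an assumption, but a plausible one.

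The comparison is within one group over time, so a bias in the 6-month mean passes straight into the estimated change. The time-point means, partial eta squared and the test are all exposed.

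**Working it through.** **1. The plan's own figure.** There is none for LOCF. The detectable effect of d = .36 to .48 belongs to the original 3-level model and does not bear on this point.

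**2. Bias when missingness is unrelated to fidelity.** Let a be the share missing only the 6-month form, b the share with baseline only, and mu0, mu3, mu6 the true means. The LOCF 6-month mean is (1 - a - b)·mu6 + a·mu3 + b·mu0, so

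bias = a·(mu3 - mu6) - b·(mu6 - mu0).

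The sign depends on the course and on the pattern of loss. Assumed examples:

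- 30/50/40%, true gain 10. a = .30: .30 × (50 - 40) = +3, gain 13. b = .30: -.30 × (40 - 30) = -3, gain 7.
- 30/40/50%, true gain 20. a = .30: .30 × (40 - 50) = -3, gain 17.
- In SD units with a = .30: 0/.5/0 turns a true change of 0 into +.15; 0/.5/.25 turns +.25 into +.325; 0/.25/.5 turns +.50 into +.425.

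Simulation reproduced the SD-unit values to rounding. Partial eta squared also moved both ways with 30% loss. For 0/.5/.25 it went from .138 to .150 (late-only) or .105 (baseline-only). For 0/.25/.5 it went from .138 to .119 or .105.

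**3. The test when true means are flat.** Inputs: n=30 from Protocol section 5a (the survey n may differ). The rest is assumed: six clinics of five, total variance 1, correlation .5 between waves, and log-odds of missing the 6-month form falling by 1 per SD of fidelity. Greenhouse-Geisser was applied throughout, with 20,000 trials per cell. The mixed model has fixed time and clinic and a therapist random intercept.

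| Late loss | Low 6-month users stop: LOCF | mixed model | Low 3-month users stop: LOCF | mixed model |
|---|---|---|---|---|
| 20% | .058 | .076 | .057 | .051 |
| 30% | .069 | .106 | .069 | .050 |
| 40% | .074 | .132 | .075 | .052 |

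With loss unrelated to fidelity, LOCF rejected in .042 to .047 of trials.

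**4. Direction at 30% loss.** A separate run split the rejections by whether the 6-month mean lay above or below baseline.

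- Low 6-month users stop: bias about +.09 SD, rejection 7.0%, of which 5.6% are false improvements against a nominal 2.5%.
- Low 3-month users stop: bias about -.09 SD, rejection 6.6%, of which 5.2% are false declines and 1.4% false improvements.

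**5. Sensitivity of the size.** For low 6-month users at 30% loss, LOCF rejects .054 at slope 0.5 and .083 at slope 1.5. A different rule, in which only therapists below the mean stop, was run at n=30. At about 20% missing, with correlations of .3 to .7, it gives 5.0 to 5.2% when the current value drives loss and 5.6 to 6.8% when the last reported value does. At about 40% missing and correlation .5 it gives 7.6% and 12.6%.

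**6. Missing baselines.** LOCF has nothing to carry into a missing baseline. With 20% of baselines missing, ANOVA power is .54 on 24 therapists against .59 for a mixed model on all 30, so the loss is small.

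**The case against.** Much of the case for the label stands in particular settings. With random loss the test keeps its level. If use also rises steadily, LOCF pulls the gain down: for assumed means of 0, .3 and .5 SD with about 40% missing at random, power is 48% against 66% with full data. If low 3-month users stop, LOCF is conservative for a claim of improvement. The inflation is small at about 20% loss, and every rate, slope and course is assumed. Aim 2 is a secondary aim of a pilot (Protocol sections 2a and 2c).

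Four stronger readings are tempting and go too far:

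- *LOCF favours a finding of improvement.* Step 4 shows that this depends on which low users stop, and the documents do not say.
- *A mixed model is the safe replacement.* It relies on missing-at-random. If low 6-month users stop (30% loss), its estimated change with flat means is +.16 against +.09 for LOCF (truth 0), and with a rise +.66 against +.51 (truth +.50). It does better if low 3-month users stop. The documents do not settle which mechanism applies.
- *The SAP claims that LOCF keeps everyone.* It speaks only of participants with partial data. The loss of therapists without a baseline is a limit of the method, not a contradiction.
- *An anonymous survey cannot be matched within person, so LOCF is impossible.* Protocol section 9b describes a study ID meant to show which documents belong together. It does not name the survey, so linkage is a separate question.

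**Conclusion.** The label is unsupported and should be corrected. LOCF can bias the 6-month mean and partial eta squared either way, by 3 points on a true gain of 10 in the worked example. That part is arithmetic; only its size rests on the assumed course and loss. For the test, the label roughly fits under random loss. It fails if low 6-month users stop responding: about 7% rejection at 30% loss, with false improvements at 5.6% against 2.5%, given n=30, correlation .5 and slope 1. If low 3-month users stop, total error is again about 7%, but in the direction of decline.

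The documents do not show that LOCF is anti-conservative, or that results under it would be wrong. They show only that its safety cannot be assumed. Confidence in the size is moderate, because no input on non-response comes from the documents.

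**What to change.** 1. Delete the word conservative and state the missing-data assumption behind the analysis.
2. In a dated amendment, add a likelihood-based mixed model on all observed survey responses: time fixed, therapist as random intercept, clinic fixed because there are only four or six. It imputes nothing and keeps therapists without a baseline. Report it beside the LOCF ANOVA, described as the analysis in the 5/5/2025 SAP update. The SAP uses the word original for the 3-level model written for dashboard data, so that term should not be used for the ANOVA.
3. Present neither analysis as conservative. Add a tipping-point analysis that lowers the unseen 6-month values on the outcome's own scale, kept within its possible range, until the conclusion changes.
4. Report missingness by time point and by pattern: late-only, baseline-only, no baseline.

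The cost is one extra model, one sensitivity analysis and a table. Fixed clinic effects use three to five degrees of freedom. The SAP says forms had already been sent, so the change may be post hoc. The amendment should say whether responses had been seen, and this is why the LOCF result stays in the report.

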#### **Aim 2: Compare MBC fidelity post IMPACT Center methods deployment versus historical controls.**

Clinic staff/Therapists (N=30; subset of 78 clinic staff/therapists in Aim 1) across 4 CMHCs in Washington state.

Inclusion: Must be aged 21+ and be working at a CMHC that is participating in the WA State CBT (Cognitive Behavioral Therapy) + Initiative.

Exclusion: Must be willing to participate in study activities

Youth: NA, there are no Youth Participants in this aim

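### Partial eta squared, the one effect size named in the updated SAP, is biased upward in small samples; a bias-adjusted value from the same ANOVA table should be reported with it

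*SAP*

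**What the plan says.** The updated plan (SAP, UPDATES paragraph) replaces the earlier mixed model with an ANOVA on the self-report survey: "A repeated-measures analysis of variance (ANOVA) will be conducted to evaluate whether fidelity to key components of MBC changes over time". There are three waves: "Descriptive statistics will be used to summarize fidelity to measurement-based care (MBC) at each of the three assessment time points". On magnitude, the only sentence is "Effect sizes (e.g., partial eta squared) will be reported to estimate the magnitude of observed effects". No bias-adjusted measure, confidence interval or mean change with an interval is named.

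The SAP gives no sample size for the survey. The Protocol gives one for Aim 2 as a whole, in section 5a ("Clinic staff/Therapists (N=30) across 4 CMHCs in Washington state") and again in section 5b ("Clinic staff/Therapists (N=30; subset of 78 clinic staff/therapists in Aim 1) across 4 CMHCs in Washington state").

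Two other provisions bear on the calculation. Under last observation carried forward, partial responders stay in: the "approach will be used, allowing participants with partial data to be retained in the analytic sample". And "If the assumption of sphericity is violated, Greenhouse-Geisser corrections will be applied".

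**The concern.** Partial eta squared is the share of time-plus-error variation that falls to time in the sample. Sampling noise alone makes that share positive, so it overstates the population share, and the overstatement grows as n falls. With about 30 respondents or fewer, it can be as large as the small effects the study might find.

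This is a pilot of the IMPACT methods, and the updated plan has no power statement and promises no interval. A reader looking for the size of the change is therefore likely to settle on this number. A non-significant result printed beside a partial eta squared of .03 invites the reading that there was a small effect the study could not confirm. At n=30, .03 is about what no effect produces.

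**Working it through.** **No figure to reproduce.** The documents give no value for partial eta squared and no power for the updated ANOVA. The d of .36 to .48 belongs to the superseded mixed-model plan. Its inputs are not fully stated, and it does not bear on this point.

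**Inputs.** Time points k=3 (SAP). n=30 (Protocol, Aim 2; assumed to apply to the survey). n=78 is the Protocol's Aim 1 count of staff and therapists (section 5b), used as a larger alternative. True effects are assumptions, labelled below.

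**No change over time.** The degrees of freedom are df1 = k−1 = 2 and df2 = (k−1)(n−1) = 2(n−1). Partial eta squared = SS_time/(SS_time + SS_error). Under no change, sphericity and independent therapists it follows Beta(df1/2, df2/2) = Beta(1, n−1). Its mean is 2/(2 + 2(n−1)) = 1/n.

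- n=30: mean 1/30 = .033; median 1 − .5^(1/29) = .024; 95th percentile 1 − .05^(1/29) = .098; chance of exceeding .01 = .99^29 = .75.
- n=78: mean 1/78 = .013.

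Simulation at n=30 (40,000 runs per case) gave .033 to .034 under two non-spherical covariances and with 30% of data carried forward. The Greenhouse-Geisser step alters the degrees of freedom and p-value, not this statistic.

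**A small true change (assumed).** Take means 0, 0.2, 0.2 in SD units and within-therapist correlation .6.

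- Grand mean .1333; sum of squared deviations .0178 + .0044 + .0044 = .0267.
- Error variance 1 − .6 = .4.
- Population value .0267/(.0267 + 2×.4) = .0323.
- Noncentrality λ = n × .0267/.4: 2.0 at n=30 and 5.2 at n=78.
- Expected partial eta squared = Σ_j Poisson(j; λ/2) × (1+j)/(n+j).

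| n | mean if no change | mean if population value is .0323 | ratio |
|---|---|---|---|
| 30 | .033 | .064 | 2.0 |
| 78 | .013 | .044 | 1.4 |

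**Other assumed true values at n=30.** .01 averages .043 (4.3 times); .02 averages .052 (2.6); .03 averages .061 (2.0); .06 averages .090 (1.5); .14 averages .165 (1.2).

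**After the change.** Partial epsilon squared = (SS_time − df1×MS_error)/(SS_time + SS_error). Because df1/df2 = 1/(n−1), this equals η² − (1 − η²)/(n−1). At η² = 1/30 and n=30 it is .0333 − .9667/29 = 0. At η² = .064 it is .064 − .936/29 = .032, back at the population value. In simulation under no change at n=30, epsilon squared averaged .000 and omega squared .0003.

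Partial omega squared, in the common form df1(F−1)/[df1(F−1) + 3n], is also centred near zero under no change, but it sits on a different scale. In the scenario above its population value is (.0267/3)/(.0267/3 + .4) = .022, not .032.

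**Limit.** With an assumed clinic-by-time correlation of .05 in 4 clinics, the null mean at n=30 rose to .044 for partial eta squared and .011 for epsilon squared. The adjustment removes small-sample bias, not clustering.

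**The case against.** Much of the opposing case stands.

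- **The statistic is only an example.** The SAP writes e.g., so a bias-adjusted measure is already allowed. That makes the change easy, but it does not tell the analyst to make it.
- **The sentence speaks of observed effects.** As a description of the sample, partial eta squared is correct. The sentence also speaks of estimating a magnitude, though, and readers commonly take such a figure as an estimate of the underlying change.
- **The survey may not be limited to 30.** N=30 covers Aim 2 as a whole, and the SAP sets no survey size. A reader might infer a very small n from the recruitment failure the SAP reports. That failure concerned entering cases with the CBT+ toolkit, and the survey was brought in because of it. Nothing in the SAP reports poor survey response, so ratios at n=20 (2.5 times) or n=12 (3.4 times) are purely hypothetical.
- **The multiplier depends on an assumed small effect.** At a true value of .14 it is only 1.2 at n=30.
- **The test is sound on this point, and raw change will be visible.** A reader might infer that the plan will declare an effect where none exists. It will not do so through this statistic: the F test does not use the biased value as an estimate, and descriptive summaries accompany it at each wave.
- **Use in planning a later study is not stated.** The documents do not say the effect size will serve that purpose; it is a plausible use, no more.

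**Conclusion.** The point holds as a minor one about estimation. Under no change, partial eta squared from this three-wave ANOVA averages 1/n: .033 if 30 therapists are analysed, .013 if 78. For an assumed 0.2 SD rise with correlation .6, it overstates the population value about 2.0 times at n=30 and 1.4 times at n=78, and less for larger effects. Nothing else in the updated plan corrects this.

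The exact 1/n result rests on independent therapists and sphericity; simulation showed little sensitivity to non-sphericity or to carrying observations forward. The sizes rest on survey numbers and true effects that the documents do not give. The documents do not support reading this as a flaw in the significance test, as a commitment to this statistic alone, or as evidence that the survey will be very small.

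**What to change.** In the UPDATES paragraph, name partial epsilon squared or partial omega squared, to be reported in place of or beside partial eta squared. Give the formula, since the two are on different scales. Partial epsilon squared is the natural companion to partial eta squared because it targets the same population quantity. Show negative estimates as they fall, not truncated at zero. State the number of therapists analysed, so that a reader can set any partial eta squared against its null expectation of 1/n.

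The cost is one phrase in the SAP and one line of R. No new data are needed, and the F test, its p-value and the analysis population do not change. The reported magnitude will be somewhat less favourable.
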